Diagnostic Accuracy of a Handheld Ultrasound vs a

Cart-Based Model: A Randomized Clinical Trial

NCT05196776

2 September 2023

Study Protocol

Study investigators utilized permuted-block randomization with an allocation ratio of 1:1. Allocation concealment included sequentially numbered, opaque, sealed envelopes. Upon enrollment, blinded study investigators selected an envelope containing study materials and prerandomized selection into the handheld device (HH) or cart-based model (CB) using Research Randomizer (Version 4.0).²⁶ Patients, who required a cardiac, lung, renal, aorta, or biliary POCUS, were randomized to a portable device, the Butterfly iQ (Guilford, CT) transducer connected to a 5th generation Apple iPad Mini (Cupertino, CA), or to a cart-based model, the GE Venue Go or GE Logiq E (Wauwatosa, WI). A PGY 1-3 emergency medicine (EM) resident performed each POCUS. An EP, credentialed in the core American College of Emergency Physicians POCUS applications, reviewed each study concurrently. Residents completed all POCUS scans prior to advanced imaging.

A cardiologist-interpreted echocardiogram, performed within 24 hours of presentation to the emergency department, served as the reference standard for cardiac images. For biliary tract images, the reference standard was a radiology-interpreted ultrasound, performed during the ED visit. For lung, renal and aortic scans, the reference standard was computed tomography images (when available and performed during the ED visit), or POCUS quality assurance review by two ultrasound fellowship trained physicians (when no CT was available)." If there was disagreement, a third ultrasound fellowship trained physician provided an interpretation. The cardiologist, radiologist, and EPs were blinded to POCUS reads.

Prior to starting their internship, our emergency medicine residents participate in an introductory five-hour introduction to POCUS course taught by our emergency ultrasound faculty. Additionally, each resident completes a three-week emergency ultrasound rotation

2

during their internship in accordance with Accreditation Council for Graduate Medical Education (ACGME) and ACEP guidelines.^{24,27} No additional training was provided to the residents prior to their study participation. Nonetheless, each participant completed more than 25 of each scan prior to participating in the study to achieve competency per ACEP and AGME guidelines.^{24,27}

Measurements

Prior to study commencement, study investigators defined the following diagnostic endpoints: ejection fraction (good >50%, moderate 30-50%, poor <30%) and the presence or absence of the following: gallstones, hydronephrosis (mild, moderate, or severe), B-lines (\geq 3 in a single lung field), and abdominal aortic aneurysm (>3cm).

Using the electronic medical record, Epic (Verona, WI), study investigators performed chart abstraction on all patients to obtain results of cardiology-interpreted echocardiograms and radiology-interpreted ultrasound and computed tomography studies.

The primary endpoint was diagnostic accuracy of each imaging modality compared to the aforementioned gold standards. The secondary endpoint of image quality was assessed by three ultrasound fellowship-trained physicians using a previously validated Likert scale assessing image quality.²⁸ A score of 1 indicated unable to interpret and a score of 7 specified superior imaging quality.

Statistical Analysis

Given the lack of pre-existing data comparing the modalities, investigators hypothesized that the cart-based model would have a 90% diagnostic accuracy versus 70% for the handheld device. We postulated that the HH would be inferior given the smaller screen size, novel technology to generate sonographic images, and limited provider experience with the device. To

3

detect a 20% difference, the sample size calculation of 98, with 49 patients randomized to each arm, was based on a power of 80% with an alpha of 0.05. We report continuous and categorical data as medians with interquartile ranges (IQR) or proportions with 95% confidence intervals (CIs) and utilized standard 2x2 tables to calculate test characteristics with 95% confidence intervals (CIs). Intraclass correlation coefficient (ICC) assessed inter-rater reliability between blinded expert reviewers, and the t-test compared median Likert scores. All analyses were performed using MedCalc (Version 19.1.6).

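### Does three-level ejection fraction, analysed alongside 2x2 tables, leave cardiac accuracy without a usable scoring rule?

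*Combined protocol and SAP*

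**What the plan says.** Cardiac is one of five scan types: "Patients, who required a cardiac, lung, renal, aorta, or biliary POCUS, were randomized to a portable device". For these scans a cardiologist-read echocardiogram "served as the reference standard for cardiac images" (Study Protocol). The Measurements section fixes the cardiac finding as "ejection fraction (good >50%, moderate 30-50%, poor <30" percent, then continues with a differently worded list, "and the presence or absence of the following: gallstones, hydronephrosis (mild, moderate, or severe", which also covers B-lines and aortic aneurysm. The same section states: "The primary endpoint was diagnostic accuracy of each imaging modality compared to the aforementioned gold standards".

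The Statistical Analysis section assumes that "the cart-based model would have a 90% diagnostic accuracy versus 70% for the handheld device". It summarises categorical results as percentages with 95% intervals and, in the same sentence, says the investigators "utilized standard 2x2 tables to calculate test characteristics with 95% confidence intervals (CIs". Neither section gives a merging rule for EF or says how a one-level miss is scored.

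**The concern.** Four of the five targets are binary as defined. Hydronephrosis also lists grades, but it falls under the present/absent wording and so has a binary rule. EF does not. If it goes into a table of scan result against reference result, two of its three levels must be merged, and the merge forgives one kind of miss: moderate/poor confusion at a 50% cut, good/moderate confusion at a 30% cut. Merging can therefore only raise EF accuracy or leave it unchanged.

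Identical reads would then support at least three accuracies: exact level, 50% cut and 30% cut. EF is the whole of the cardiac component of the primary endpoint, so an unstated choice could move both the reported accuracy and the handheld-versus-cart difference.

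**Working it through.** **The plan's own figure.** The sample size is given "with 49 patients randomized to each arm, was based on a power of 80% with an alpha of 0.05". For 90% vs 70% with pooled variance and one-sided alpha 0.05: n = [1.645·√(2·0.8·0.2) + 0.842·√(0.09 + 0.21)]² / 0.20² = 48.4, so 49 per arm and 98 in all. The figure reproduces one-sided; two-sided it would be 62 per arm. Sidedness is a separate matter. The 90% and 70% are not tied to any way of scoring EF, so a merged score cannot be shown to depart from what was hypothesised.

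**Inputs.** The three levels, 90% vs 70% and 49 per arm come from the documents. The EF mix, the error rates, the cardiac share and the pooling of the five scan types are all assumptions.

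**Effect on EF accuracy.** Let g, m and p be the shares of good, moderate and poor on the reference, and e the error rate. All errors are to a neighbouring level, and moderate errors split evenly. Exact accuracy is 1 − e.

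- Gain at the 50% cut: e(m/2 + p)
- Gain at the 30% cut: e(g + m/2)

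| Mix g/m/p | 50% cut, e = 10% / 30% | 30% cut, e = 10% / 30% |
|---|---|---|
| 80/15/5 | 1.25 / 3.75 points | 8.75 / 26.25 points |
| 50/30/20 | 3.5 / 10.5 | 6.5 / 19.5 |
| 34/33/33 | 4.95 / 14.85 | 5.05 / 15.15 |

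**Effect on the EF difference.** Take exact EF accuracy as 90% (cart) and 70% (handheld). The 20-point gap becomes 20 minus the difference in gains. In the same mix order:

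- 50% cut: 17.5, 13.0, 10.1
- 30% cut: 2.5, 7.0, 9.9

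**Effect on a pooled difference.** With cardiac share s and the other scans also at 90% vs 70%, the pooled gap is s × (EF gap) + (1 − s) × 20.

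- s = 20%: 18.0-19.5 (50% cut), 16.5-18.0 (30% cut)
- s = 40%: 16.0-19.0 (50% cut), 13.0-16.0 (30% cut)

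**Precision.** The 95% half-width for the difference at 90% vs 70% is 1.96·√(0.30/n). At n = 49 it is 15.3 points. With 20-40% cardiac scans there are 49 × 0.2 = 9.8 to 49 × 0.4 = 19.6 per arm, and the EF-only half-width is about 34 to 24 points.

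**Whether the text conflicts with itself.** The plan lists EF apart from the present/absent findings, provides percentages with intervals for categorical data, and never says that EF goes into a 2x2 table. Read together, these give a consistent analysis: percent in the correct level for EF, and 2x2 tables for the four binary targets. A 2x2 table of arm by correct/incorrect would merge no levels at all.

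**The case for a change.** The strongest reply is that allowing a rule is not the same as stating one. Test characteristics most naturally means sensitivity and specificity from a scan-by-reference table, and the sentence on percentages does not define a correct EF read.

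Nor need merging only shrink the difference. With a 50/30/20 mix, suppose all the cart's 10% errors are moderate/poor and all the handheld's 30% errors are good/moderate. At the 50% cut the arms score 100% and 70%, a gap of 30. At the 30% cut they score 90% and 100%, which reverses the direction. Pooled with other scans at a 20-point gap, a 20% cardiac share gives 0.2 × 30 + 0.8 × 20 = 22 or 0.2 × (−10) + 0.8 × 20 = 14. A 40% share gives 24 or 8. One sentence would close the gap.

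The omission stands, and so does the arithmetic. The extreme case is a bound: it needs the two arms to err at wholly different boundaries, and nothing in the documents points that way. The 26-point gain and the 2.5-point EF gap both come from one corner of the grid, with 80% good EF and a 30% cut; the gain needs a 30% error rate, and the gap sets 30% against 10%. The benefit of adding a rule is also limited by timing. The Statistical Analysis section is in the past tense, so if EF results have been analysed, a rule added now would be post hoc.

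**Conclusion.** No change to the plan is called for. It leaves a scoring detail unstated; it does not prescribe a wrong analysis. Scoring EF by exact level follows from the three levels defined in advance and fits the reporting already described. A cut at 50% is a conventional alternative, and statisticians may reasonably differ on which to prefer.

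The gap touches one scan type of five, and its effect cannot be sized from the documents because they give no EF mix, error rates or cardiac share and do not state that scan types are pooled. On assumed values with similar error patterns in both arms, a 50% cut takes a 20-point pooled difference to 16.0-19.5 points, a shift of at most 4 points against a half-width of about 15. A 30% cut shifts it by up to 7 points, and the contrived opposite-error case by up to 12 (20 to 8). It is a minor reporting gap that an analyst would fill sensibly.

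### 80% power with 49 per arm holds only for an undisclosed one-sided 5% test; at two-sided alpha 0.05 power is about 70%

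*Combined protocol and SAP*

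**What the plan says.** All the relevant text is in the Statistical Analysis section of the combined protocol and SAP, apart from the 1:1 allocation, which is in the Study Protocol section.

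- Assumed accuracies: "investigators hypothesized that the cart-based model would have a 90% diagnostic accuracy versus 70% for the handheld device".
- Target and total: "detect a 20% difference, the sample size calculation of 98".
- Split, power and error level: "with 49 patients randomized to each arm, was based on a power of 80% with an alpha of 0.05".
- Direction: the investigators expected the handheld to do worse and gave reasons, but they do not declare a one-sided test.
- Intervals: the plan reports "proportions with 95% confidence intervals (CIs", and uses the same 95% level for the test characteristics from the 2x2 tables. No other interval level appears.

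The section does not give the sidedness of alpha, the sample size formula, the test for the between-arm comparison of accuracy, or any allowance for dropout.

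**The concern.** Two accuracies, an alpha, a power and an allocation ratio fix the sample size once sidedness is known, so the figure can be checked. An alpha of 0.05 with no qualifier is ordinarily read as two-sided. On that reading, 49 per arm is too small for 90% versus 70% at 80% power.

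Diagnostic accuracy is the primary endpoint, and the trial asks whether the handheld performs worse. If the arms do not differ significantly, readers will weigh that result against the stated 80% power. If the power is really nearer 70%, a finding of no difference will look more reassuring about the handheld than the design allows.

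**Working it through.** **Inputs (Statistical Analysis section).** p1 = 0.90, p2 = 0.70, difference d = 0.20, alpha = 0.05, power = 0.80, n = 49 per arm. Allocation is 1:1 (Study Protocol section). No dropout allowance is stated, so none is applied.

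The mean proportion is 0.80. The null variance term is 2 × 0.80 × 0.20 = 0.32. The alternative variance term is 0.90 × 0.10 + 0.70 × 0.30 = 0.30. For 80% power, z_b = 0.842.

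**Step 1: reproduce the plan's figure.** The pooled-variance formula is

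n per arm = (z_a × √0.32 + z_b × √0.30)² / 0.20²

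With one-sided alpha 0.05, z_a = 1.645:

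n = (0.931 + 0.461)² / 0.04 = 48.4, rounded up to 49 per arm, 98 in total.

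This matches the plan exactly.

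**Step 2: the same formula, two-sided.** With z_a = 1.960:

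n = (1.109 + 0.461)² / 0.04 = 61.6, rounded up to 62 per arm, 124 in total.

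**Step 3: could another two-sided formula give 49?**

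| Two-sided formula, alpha 0.05, 80% power | n per arm |
|---|---|
| Unpooled variance | 58.9 → 59 |
| Arcsine | 59.01 → 60 |
| Pooled variance | 61.6 → 62 |
| Unpooled, continuity-corrected | 68.5 → 69 |
| Pooled, continuity-corrected | 71.2 → 72 |

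None does. The smallest, 59, is 10 per arm above the plan's figure.

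**Step 4: power with 49 per arm.** The pooled normal approximation is

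power = Φ[(0.20 − z_a × √(0.32/49)) / √(0.30/49)]

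with √(0.32/49) = 0.0808 and √(0.30/49) = 0.0782.

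- Two-sided: (0.20 − 1.960 × 0.0808) / 0.0782 = 0.532, so power = 70.3%.
- One-sided: (0.20 − 1.645 × 0.0808) / 0.0782 = 0.857, so power = 80.4%.

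Because the plan names no test, the other candidates are shown too:

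| Method, n = 49 per arm | Two-sided 0.05 | One-sided 0.05 |
|---|---|---|
| Pooled normal approximation | 70.3% | 80.4% |
| Unpooled normal approximation | 72.4% | 81.9% |
| Arcsine approximation | 72.3% | 81.8% |
| Continuity-corrected approximation | 60.7% | 72.5% |
| Exact enumeration, uncorrected chi-square | 72.5% | 81.4% |
| Exact enumeration, Fisher's exact test | 62.7% | 74.4% |

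No two-sided entry reaches 80%. The one-sided entries reach it only for uncorrected tests.

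**Step 5: what 49 per arm can detect.** At two-sided 0.05, the pooled approximation gives 80.1% power for 90% versus 67%, a 23-point difference. Exact enumeration of the uncorrected chi-square test gives 80.6% at 90% versus 67.5%, a 22.5-point difference.

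**The case against.** The strongest reply is that this is an omission and not a miscalculation. Under one ordinary formula 49 per arm is exactly right, a one-sided test does have an alpha of 0.05, and the stated expectation that the handheld would be inferior fits a one-sided calculation. The 95% intervals are planned for proportions and test characteristics, not for the between-arm difference, and per-arm 95% intervals can sit beside a one-sided comparison. The two-sided power also depends on a test that the plan does not name: the miss rate is 27.5% for the uncorrected chi-square and 37.3% for Fisher. Finally, the document is written largely in the past tense, so the correction changes only how a result is read.

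Part of this stands. The one-sided basis is inferred from the numerical match and not documented. The 95% intervals support a two-sided reading without proving it. A single power figure should name its method.

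The rest does not rescue the text. Expecting a direction is not the same as declaring a one-sided test, and the sample size sentence speaks only of detecting a difference. If a one-sided test was meant, the plan leaves out the one parameter needed to reproduce its own sample size and offers no interval or bound that corresponds to that test. Naming the test would move the two-sided figure within roughly 61% to 72%, but not to 80%.

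**Conclusion.** The concern holds. The stated alpha, power, accuracies and sample size agree only if the test is one-sided at 5% and uncorrected, which the plan does not disclose. On the ordinary two-sided reading, 49 per arm gives about 70% power (60.7% to 72.5% depending on the method), and 80% power would need 62 per arm by the pooled formula. The risk of missing a true 90% versus 70% difference is then about 30%, not 20%.

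This rests on the plan's own assumed accuracies, one independent observation per patient, equal arms and no dropout. It must be corrected, because the power claim supports the primary endpoint and is not met as a reader would understand it.

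**What to change.** Restate the sample size sentence without enrolling more patients.

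**Preferred wording:** With 49 patients per arm, power is about 70% at two-sided alpha 0.05 (pooled normal approximation) to detect 90% versus 70% accuracy; 80% power is reached for a difference of about 23 percentage points (90% versus 67%).

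**Alternative, if a one-sided test was intended:** state that alpha is one-sided 0.05 and base the primary inference on a one-sided 95% bound for the between-arm difference, which is the corresponding limit of a two-sided 90% interval. The interval then matches the test.

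In either case, name the formula and the test for the between-arm comparison, since the power figure depends on them.

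The cost is one sentence in the sample size paragraph; the alternative also adds the bound for the difference. The stated power becomes less favourable, or the one-sided test becomes visible.

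### The trial is sized for a 90% versus 70% between-arm difference in accuracy, but no between-arm estimate, test or sidedness is stated, and two-sided power at 49 per arm is about 72%, not 80%

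*Combined protocol and SAP*

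**What the plan says.** The Study Protocol section describes 1:1 randomization of patients to a handheld or a cart-based device. The Measurements section words the primary endpoint device by device: "The primary endpoint was diagnostic accuracy of each imaging modality compared to the aforementioned gold standards". It also says that the diagnostic endpoints were defined before the study began, and lists them: "ejection fraction (good >50%, moderate 30-50%, poor <30%) and the presence or absence of the following: gallstones, hydronephrosis (mild, moderate, or severe"), followed by B-lines and aortic aneurysm.

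The Statistical Analysis section assumes 90% accuracy for the cart and 70% for the handheld, gives a directional rationale ("We postulated that the HH would be inferior given the smaller screen size"), and states that the "sample size calculation of 98, with 49 patients randomized to each arm, was based on a power of 80% with an alpha of 0.05".

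For accuracy, the stated analysis is proportions with 95% confidence intervals, and the investigators "utilized standard 2x2 tables to calculate test characteristics with 95% confidence intervals (CIs"). An intraclass correlation covers rater agreement. The one comparison between groups that is named concerns the secondary endpoint: "the t-test compared median Likert scores". The words one-sided and two-sided do not appear.

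**The concern.** The sample size presupposes a comparison of two independent proportions, but the analysis described for accuracy stops at each device against its reference standard. Followed as written, it produces two sets of test characteristics with separate intervals, and no stated quantity that answers the randomized question.

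The missing sidedness matters because the sample size depends on it. A reader who sees alpha 0.05 beside 95% intervals will assume a two-sided test and believe the power is 80%. If that reading is right, the stated power is not delivered. If a one-sided test was meant, the power is right, but the 95% intervals do not match the test and the reader has not been told. Results in the range the trial might plausibly produce would be significant under one reading and not under the other.

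A smaller gap sits beside this one: ejection fraction has three levels, and the plan does not say how these enter a 2x2 table.

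**Working it through.** **Inputs, all from the Statistical Analysis section:** p1 = 0.90 (cart), p2 = 0.70 (handheld), difference d = 0.20, alpha 0.05, power 80%, 49 per arm. Derived: mean proportion 0.80; pooled variance term 2 × 0.80 × 0.20 = 0.32; unpooled term 0.90 × 0.10 + 0.70 × 0.30 = 0.30. Normal quantiles: 1.645 (one-sided 0.05), 1.960 (two-sided 0.05), 0.842 (80% power).

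**Step 1. Reproduce 49 per arm.** Pooled formula: n = [(z_alpha × √0.32 + z_power × √0.30) / 0.20]².

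- One-sided: [(0.9305 + 0.4610) / 0.20]² = 48.40, rounded up to 49. This matches the plan.
- Two-sided: [(1.1087 + 0.4610) / 0.20]² = 61.60, rounded up to 62.

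Other common formulas, per arm at 80% power and alpha 0.05:

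| Formula | One-sided | Two-sided |
|---|---|---|
| Pooled z | 48.40 → 49 | 61.60 → 62 |
| Unpooled z | 46.37 → 47 | 58.87 → 59 |
| Arcsine | 46.48 → 47 | 59.01 → 60 |
| Pooled, continuity-corrected | 57.97 → 58 | 71.25 → 72 |

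Using the pooled variance in both terms gives 49.46 (50) one-sided and 62.79 (63) two-sided. No two-sided 0.05 formula comes near 49, so rounding does not explain the figure.

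**Step 2. Other routes to 49.** With the pooled formula, two-sided 0.05 at 70% power gives 48.7, rounded up to 49. Two-sided alpha 0.10 at 80% power is numerically the same calculation as one-sided 0.05 and also gives 49. A misstated power or alpha would therefore produce the same number.

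**Step 3. Two-sided power at 49 per arm.** Pooled formula: Φ[(0.20 × √49 − 1.960 × √0.32) / √0.30] = Φ[(1.4000 − 1.1087) / 0.5477] = Φ(0.532) = 70.3%. Exact enumeration over Binomial(49, 0.90) × Binomial(49, 0.70), uncorrected pooled z test: 72.5% two-sided and 81.4% one-sided.

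**Step 4. How often sidedness decides.** In the same enumeration, 8.9% of trials are significant one-sided but not two-sided. Example: 44/49 versus 37/49. The difference is 7/49 = 14.3 points and the pooled proportion is 81/98 = 0.8265, so z = 0.1429 / √(0.8265 × 0.1735 × 2/49) = 1.867. One-sided p = 0.031; two-sided p = 0.062. The Newcombe 95% interval is −0.9 to 29.1 points and the 90% interval is 1.6 to 26.7 points.

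**The case against.** The strongest reply is that this is a reporting gap. The arms are independent, so a reader given both accuracies and their denominators can derive the difference and an interval. If a one-sided test was intended, the sample size and power are correct and agree with the directional hypothesis, and only a word is missing. It is true that no information is lost. But a contrast that each reader builds for themselves is not a stated primary analysis, and the text does not let anyone tell which case applies.

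Several stronger readings are tempting, and the documents do not support them.

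- **That the trial was designed as one-sided.** The directional sentence fits this, but Step 2 shows that a misstated power or alpha fits 49 as well.
- **That nothing was fixed in advance.** The Measurements section says the diagnostic categories were defined before the study began. What carries no date is the contrast, the test, the sidedness and the handling of three-level ejection fraction.
- **That hydronephrosis scoring and the unit of analysis are open.** Hydronephrosis is listed under presence or absence and 2x2 tables are used, so any grade versus none is the natural reading. Patients were randomized ("Patients, who required a cardiac, lung, renal, aorta, or biliary POCUS, were randomized") and the sample size counts patients, so one result per patient is also the natural reading.
- **That the scoring rule alone could overturn a result.** Starting from 44/49 versus 34/49 (two-sided p = 0.012), re-scoring three handheld patients as correct gives p = 0.062. But a rule applies to both arms. Re-scoring the same share of errors in each (1 of 5 cart, 3 of 15 handheld) gives 45/49 versus 37/49, two-sided p = 0.029.
- **That sidedness was chosen after the data were seen.** The section is written in the past tense ("All analyses were performed using MedCalc (Version 19.1.6")), but nothing in it suggests this.

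**Conclusion.** The point holds. The comparison that sets the sample size has no stated between-arm estimate, interval, test or sidedness, and the stated 80% power is not reached under two-sided 0.05, the reading that matches the plan's own 95% intervals. Two-sided power is about 70% by the pooled formula and 72.5% exact, and 80% would need 59 to 72 per arm depending on the formula (62 pooled). One-sided, exact power is 81.4%. If accuracy really is 90% and 70%, about 9% of trials would have a conclusion that turns on the unstated sidedness.

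These figures assume one result per patient, 49 analysed patients in each arm, the plan's own 90% and 70%, and for the exact powers an uncorrected z test. The statement that only the one-sided pooled calculation gives 49 holds for the formulas tried, at the stated power and alpha. Which sidedness was intended remains unknown.

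**What to change.** State as the primary analysis the between-arm difference in the proportion of patients correctly classified against the reference standard, cart minus handheld. Give it a 95% confidence interval (Newcombe is suitable) and one named two-proportion test. Count ejection fraction as correct when its level matches the reference, and score hydronephrosis as presence or absence. Say that the test governs the conclusion: under the planning assumptions the Newcombe 95% interval and the uncorrected two-sided z test disagree in about 1.4% of trials. Keep the 2x2 results by device as descriptive.

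State the sidedness and align the power with it:

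- If one-sided 0.05 was intended, say so, give power of about 81%, and show the 90% interval beside the 95% interval.
- If two-sided 0.05 is used, restate power at 49 per arm as about 72%, without enrolling more patients.

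Cite a dated record from before outcome data were seen that fixes the contrast, test and sidedness. If there is none, label them as specified afterwards and report both p-values.

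The cost is a few sentences and one extra line of analysis, with no new data. The two-sided choice exposes a power below the stated 80%; the one-sided choice cannot support a claim that the handheld is better. The uncorrected test can be slightly liberal two-sided: its exact size is 4.9% to 5.9% when both arms share an accuracy between 70% and 90%. If outcomes have already been seen, the change gives transparency but cannot restore pre-specification.

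### The image-quality t-test compares means while the plan summarises by medians; no between-arm difference or CI is planned, and the unit of analysis for three reviewers' scores is unstated

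*Combined protocol and SAP*

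**What the plan says.** The Measurements section of the combined protocol and SAP names one secondary endpoint and its raters: "The secondary endpoint of image quality was assessed by three ultrasound fellowship-trained physicians using a previously validated Likert scale". The scale has seven points: "A score of 1 indicated unable to interpret and a score of 7 specified superior imaging quality".

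The Statistical Analysis section then says four things that bear on it:

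- General summary rule: "We report continuous and categorical data as medians with interquartile ranges (IQR) or proportions with 95% confidence intervals (CIs").
- Accuracy: the investigators "utilized standard 2x2 tables to calculate test characteristics with 95% confidence intervals (CIs").
- Reviewer agreement: "Intraclass correlation coefficient (ICC) assessed inter-rater reliability between blinded expert reviewers".
- Between-arm comparison of image quality: "the t-test compared median Likert scores".

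Confidence intervals are thus stated for proportions and for test characteristics. Neither section mentions a mean score, a difference between arms in image quality, or an interval for such a difference. Neither says how three reviewers' ratings of one scan enter the t-test.

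**The concern.** A t-test yields a p-value about arm means. If the arms are described by medians, the reader has a p-value about one quantity and a summary of another, with nothing to show how large the difference is. On a scale of 1 to 7, sample medians often tie or jump by a whole point. Identical medians can therefore stand beside a significant result, and medians a point apart beside a non-significant one.

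The second issue is the unit of analysis. Three ratings of the same scan are correlated. A t-test on one score per scan is sound; a t-test on all ratings as if independent is not. The wording leaves this open.

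This is the only outcome for which the plan names a between-arm test. At stake is what can be concluded about image quality, not about diagnostic accuracy.

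**Working it through.** **Inputs from the documents.** Scale 1 to 7; three reviewers; 49 patients per arm; alpha 0.05. **Assumed, because the documents give no score data:** one scan per patient, the score distributions, the correlation between reviewers, and a two-sided test.

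**The plan's own figure.** There is none for image quality. The total of 98 belongs to the primary endpoint (90% versus 70%, power 80%). With pooled variance, n per arm = [z_α √(2 × 0.8 × 0.2) + 0.842 √(0.09 + 0.21)]² / 0.2². A one-sided z_α of 1.645 gives (0.931 + 0.461)² / 0.04 = 48.4, so 49 per arm and 98 in total. A two-sided 1.96 gives 61.6, so 62 per arm. The sidedness is a separate matter; nothing below depends on it.

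**Step 1: what the test compares.** The statistic is t = (mean_A − mean_B) / [s √(1/49 + 1/49)]. Only arm means enter. If each scan is first reduced to the median of its three ratings, the numerator is the difference between arm means of those medians, still not the difference between the group medians. The mismatch holds on either reading.

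**Step 2: the unit of analysis.** Three ratings per scan give 49 × 3 = 147 per arm. If they are treated as independent, the true variance of the arm mean exceeds the assumed one by 1 + (3 − 1) × ICC, so the false-positive rate is about 2 × Φ(−1.96 / √(1 + 2 × ICC)).

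| Assumed ICC | Variance factor | 1.96 / √factor | Formula | Simulated, scores rounded to 1–7 |
|---|---|---|---|---|
| 0.5 | 2.0 | 1.386 | 16.6% | about 16% |
| 0.7 | 2.4 | 1.265 | 20.6% | about 20% |

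With one score per scan, whether average or median, the simulated level with equal arms was about 5%.

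**Step 3: how often medians and p-value part company (illustration only).** Ninety-six assumed pairs were simulated with 49 scores per arm: normal scores rounded and clipped to 1–7, SD 1.0 to 1.6, shift 0.5 to 1.0, 20,000 trials each.

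- Significant t-test with identical sample medians: 0.4% to 56% of trials; median pair 9.5%, middle half 4% to 16%.
- Medians at least one point apart with a non-significant t-test: 0% to 39%; median pair 8%.

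**Step 4: can an estimate be given?** The 95% half-width for a mean difference is t(0.975, 96 df) × SD × √(2/49) = 1.985 × 0.202 × SD = 0.401 × SD. That is 0.40 points at SD 1.0 and 0.60 at SD 1.5. In the 96 pairs the interval covered the true mean difference in 94.7% to 95.3% of trials.

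**Step 5: average or median of the three reviewers.** Six cases with three ratings per scan were simulated (ICC 0.5 and 0.7 with three assumed pairs of arm means).

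| One score per scan | Power | CI half-width | Significant with identical group medians |
|---|---|---|---|
| Average of three | 76–93% | 0.39–0.48 | 0.4–1.1% |
| Median of three | 73–89% | 0.42–0.51 | 2.7–32% |

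The average has about 2 to 5 percentage points more power.

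**The case against.** **The wording has a benign reading.** The same sentence concerns agreement between reviewers, so the median may be the per-scan median over the three. The t-test would then be legitimate, and a descriptive median beside a test of means is common. This stands as to validity. It does not supply the missing difference and interval, and the per-scan reading still has to be guessed.

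**The mismatch rates do not measure harm from the t-test.** This stands. In a smaller rerun of the 96 pairs (3,000 trials each), significance beside identical medians occurred in 0.5% to 58% of trials with the t-test (median pair 9.6%) and in 0.5% to 56% with the Wilcoxon rank-sum test (median pair 8.5%). The rates mainly show how coarse a median is on seven points. They support adding an estimate, not replacing the test. With every shape assumed, so wide a range is illustrative at most.

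**Some of this is inferred.** The summary rule is generic and does not name the Likert score, and the word p-value does not appear. Both are fair, but the comparison sentence itself speaks of median Likert scores, and a test implies a p-value.

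**Stronger readings.** A reader might infer that a t-test is invalid on a seven-point scale. The simulated level of about 5% with one score per scan speaks against that. A reader might also infer that ratings were pooled and the error rate was 16% to 20%. The documents do not say so; they only fail to exclude it.

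**Conclusion.** The point holds as a minor one on reporting and specification. Two parts rest on the text alone: the named test does not refer to the stated summary, and no between-arm estimate or interval is planned for the only secondary endpoint. The third part is conditional. The t-test is valid as a comparison of means if each scan contributes one score, and the plan does not state this. The size of that risk, a false-positive rate of about 16% to 20% instead of 5%, assumes ICCs of 0.5 to 0.7, one scan per patient and all 147 ratings per arm entered as independent. It is the cost of one possible analysis, not a finding that it was carried out. The primary accuracy analysis and the sample size of 98 are untouched.

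**What to change.** In the Statistical Analysis section:

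1. State that each scan contributes one image-quality score, the average of the three reviewers.
2. Describe the t-test as a comparison of mean scores between arms.
3. Report the arm means with the mean difference and its 95% CI.
4. Keep medians with interquartile ranges as description only.

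This takes a few sentences and one added estimate, from ratings already planned. The t-test is kept. In the assumed cases, averaging gains a little power over the per-scan median and narrows the interval slightly. If ratings were in fact analysed individually, the comparison would have to be rerun on one score per scan.
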